Local inflammation in the region of the lumbar sensory ganglia plays a role in many forms of low back pain, including those forms involving pathology of the intervertebral discs^{10,11}. A common treatment for some forms of low back pain is local injection of corticosteroids. Randomized clinical trials of such treatments have often suggested that steroid injections are effective only in the short term^{12,13}. The nominal target of anti-inflammatory corticosteroid drugs is the glucocorticoid receptor (GR). However, recent in vitro studies show that many clinically used steroids (including those commonly used for back pain, e.g. 6- α methylprednisolone and triamcinolone) can also activate the mineralocorticoid receptor (MR) with similar potency^{1,2}. The MR was originally viewed only as the target of aldosterone, promoting sodium reabsorption in the kidney. However, this receptor has been detected in other cell types including peripheral sensory neurons¹⁴. In many tissues, MR activation is pro-inflammatory^{3,4}. Some pro-inflammatory effects may be due to receptors in macrophages, where MR activation promotes production of pro-inflammatory cytokines and tissue destruction, while GR activation promotes tissue remodeling and wound repair¹⁵. We hypothesize that adding an oral MR blocker, eplerenone, at the time of steroid epidural injections for low back

pain due to lumbar degenerative disc disease, will improve response to the injected corticosteroids.

Eplerenone is chosen as a more specific MR blocker than its predecessor, spironolactone¹⁶, avoiding side effects such as gynecomastia and sexual dysfunction. It is currently approved for use in the US as a therapy for high blood pressure and for heart failure. Its effectiveness in heart failure is thought to be due in part to anti-inflammatory effects in cardiac tissue¹⁵.

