Patients are normally seen for follow-up approximately one month after an epidural injection. Subjects who are recommended to have a second epidural injection at this follow-up visit will receive a second dose of the same study medication they received after their first injection. The same protocol will be followed: such subjects will have a repeat blood draw and re-confirmation of inclusion parameters prior to restarting the medication. Subjects who become ineligible at the time of the second injection will not receive a second round of study medication, but will continue to complete questionnaires and their data will be retained for analysis.

All patients will receive the same epidural steroid and approach (interlaminar injection of Kenalog (triamcinolone) and saline) as part of their standard care. Triamcinolone has a substantial potency for the MR in addition to the GR; all of the steroids commonly used for epidural injections show some activity at the MR². The procedures and drug are routinely used at the participating clinics for treatment of degenerative disc disorders. We will use the REDCap (Research Electronic Data Capture) system for secure web based capture of questionnaire data, which is required in order to protect the

confidentiality of the subjects' data. This is provided by the Center for Clinical and Translational Science and Training. We already use this system for another project.

7. Research data collection/study procedures:

Patients meeting criteria will be invited to participate in the study prior to their first epidural steroid injection. If they consent, they will complete the Oswestry Low Back Pain Questionnaire (version 2) just prior to their first injection. This instrument is commonly used for research and is well-validated²⁰. It is completed by the patient and captures the functional effects of back pain on various activities, providing a more meaningful picture than a simple static pain rating.

The patients will complete the Oswestry Low Back Pain Questionnaire again four weeks after their first injection, a time point at which patients routinely have a follow-up visit. Patients referred for a second injection at this time will complete an additional Oswestry just prior to that injection. The research nurse will contact the patients for additional follow-up at 3 months, 6 months, 1 year after their epidural injection (or after their second epidural injection if this is recommended).

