Patients recruited to participate will undergo the clinically indicated lumbar epidural steroid injection as part of their treatment regimen, considered standard of care. Additionally, they will concurrently receive the study drug or placebo for ten days. Patients who have met all inclusion criteria, including a basic metabolic panel with potassium and creatinine within normal limits, are expected to have low risk of adverse effects from the study drug - eplerenone. However, participants will be informed of potential side effects, including but not limited to dizziness, fatigue, abdominal pain, and diarrhea, and instructed to call study physician to discuss evaluation and/or discontinuation.

An interim analysis will be conducted halfway through the study (after 20 subjects are enrolled) to ensure there are no unexpected adverse responses to eplerenone. [name], a department physician not involved with the study, will review subjects' records for safety issues on an ongoing basis.

12. Data Analysis:

The primary analysis will be to compare the change (difference score) in the Oswestry Disability Index between the placebo and eplerenone groups at each time point. Scores on this instrument range from 0 to 100%. With 20 subjects per group, a difference of 9 points in score can be detected with 80% power and $\alpha = 5\%$, assuming a standard deviation of 10. This value of standard deviation has been observed in similar studies²⁰. Some studies have considered a difference of 4 points to be clinically significant while others have used higher values, up to 15 (the value used by the FDA in evaluating one back pain procedure). Average differences of 15 have been reported in studies of sciatica and chronic back pain²⁰. Thus although the sample size is small it should be large enough to detect large or moderately sized clinically significant differences

between the groups. The Mann-Whitney test will be used to evaluate the significance of differences between the two groups, as the Oswestry is an ordinal scale.

Primary outcome measure: The change from the pre-injection Oswestry Disability Index scores for low back pain and disability at the selected time points.

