Statistical Analysis Plan

Epidural Steroid Injection with Supplemental Oral Eplerenone for Low Back Pain: A Prospective, Double Blind Randomized Trial

Principal Investigator: [name]

Project Sponsor: Department of Anesthesiology, University of Cincinnati College of Medicine

UC IRB Number: 2017-2713

[figure not shown]
IRB Approval Date(s): 10/11/2017

SAP Date (PI Signature Date): 1-17-18

Version: Original

Statistician(s): [name]

[figure not shown]
This SAP has been reviewed and approved by:

[name], Principal Investigator

1-17-2018

Date

[name], Statistician

1-17-2018

Date

A. Introduction:

Low back pain is a leading cause of disability and health care costs in the United States, and treatments are ineffective for many patients. Epidural steroid injections are a common treatment, but their efficacy has been questioned and for many patients they do not provide complete relief. We hypothesize, based on preclinical studies, that lack of complete efficacy may be due to the fact that clinically used steroids activate not only the intended drug target, the glucocorticoid receptor (GR), but also the pro-inflammatory mineralocorticoid receptor (MR). To test this hypothesis, this pilot study will recruit patients scheduled for lumbar epidural steroid injections for degenerative disc disease, and randomize them to receive a concurrent treatment with oral eplerenone (a clinically approved antagonist of the mineralocorticoid

receptor) or placebo for 10 days starting just after the epidural injection. The primary outcome will be improvement in treatment outcome as measured by the Oswestry Low Back Pain Disability Questionnaire, a validated research instrument that investigates both pain and functional outcomes. Subjects will be followed for one year. Secondary outcomes include the clinical course, in particular, whether the patient requires additional injections or not as part of their routine clinical care.

B. Specific Aims and Hypotheses

Aim 1: Test the hypothesis that subjects receiving eplerenone will show greater improvement in the Oswestry Low Back Pain Disability Questionnaire 12 months after the epidural steroid injection than subjects receiving placebo (primary outcome measure).

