Aim 2: Test the hypothesis that subjects receiving eplerenone will show greater improvement in the Oswestry Low Back Pain Disability Questionnaire at earlier time points (2 weeks, 3, and 6 months after the epidural steroid injection) than subjects receiving placebo.

Aim 3: test the hypothesis that subjects receiving eplerenone will have better clinical outcome of their epidural steroid injection than subjects receiving placebo.

C. Study Design

The University of Cincinnati Department of Anesthesiology has two suburban pain clinics that will serve as sources for recruiting subjects, UC Health Pain Medicine Center (Midtown) and UC Health Pain Medicine Center (West Chester).. Our target number for study enrollment is 40 subjects (20 per group). We have obtained authorization for 60 subjects, in order to allow for subjects who drop out. Patients evaluated for degenerative disc disease are routinely given an epidural steroid injection as part of their treatment regimen. Often this is the preferred treatment; if there is no clear indication for surgical intervention, a more conservative approach is sought prior to considering surgery.

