- Treated with oral steroids or injectable steroid within the past year.
- Diabetic
- Systolic blood pressure reading less than 100 mm Hg at most recent clinic visit.
- Prescribed protease inhibitors, a class of antiviral drugs widely used to treat HIV/AIDS and Hepatitis C.
- Taking strong CYP3A4 inhibitors
- Taking potassium supplements or potassium-sparing diuretics (amiloride, spironolactone, or triamterene) or using salt substitutes that contain potassium
- Lactating.
- Pregnant
- .

D. Statistical Analysis Plan

For categorical variables, counts and percentages will be presented. As a check on randomization, groups will be compared using the Fisher's exact test. For continuous variables, mean, median, standard deviation (SD) and inter-quartile range (IQR) will be presented. Groups will be compared using the t-test, except that non-parametric methods will be used for ordinal variables or variables distributed non-symmetrically.

D1. Aims 1 and 2:

Each Oswestry response has 6 ordinal response choices scored 0 through 5. With 10 items and with the lowest score (0) representing the least disability, the total raw score ranges from 0 to 50. The score is expressed as a percentage of the maximum possible score. If a subject omits one question, the percentage score is based on a maximum score of 45. If a subject omits more than one question the questionnaire is considered invalid and the data not used. Improvement scores are calculated by subtracting the score at a given time point from the score obtained prior to the first epidural steroid injection. Group differences in the improvement scores at the 12 month time point and at the intermediate time points will be analyzed using the Mann-Whitney test.

Patients who are withdrawn from the study due to the initial blood test results will be considered as screening failures; no follow-up data or questionnaire scores will be obtained.

D2. Aim 3: The clinical outcome of the first epidural steroid injection will be abstracted from the medical chart record of the follow-up visit that occurs approximately 1 month after the injection, and will be summarized as an ordinal variable scored as: 1 adequate pain relief, no further treatment recommended; 2, partial relief, second injection recommended; 3 little pain relief, alternative treatment recommended.

Demographic data will be compared between the groups to determine if values differ significantly despite randomization (table 1 below).

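### The protocol makes the Oswestry change at every visit primary, the SAP only the 12-month change, and neither document says which governs

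*Protocol*

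**What the plan says.** **Protocol.** Section 12 describes the primary analysis as to "compare the change (difference score) in the Oswestry Disability Index between the placebo and eplerenone groups at each time point". Its outcome line reads "The change from the pre-injection Oswestry Disability Index scores for low back pain and disability at the selected time points". Sections 7 and 16 list the visits (4 weeks, 3 months, 6 months, 1 year), but none is named as the primary one. The power statement in Section 12 (20 per group, 9 points, SD 10, 80% power, 5% alpha) is tied to no visit.

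**SAP.** Section B, Aim 1, states the hypothesis for improvement "12 months after the epidural steroid injection than subjects receiving placebo (primary outcome measure"). Aim 2 covers improvement "at earlier time points (2 weeks, 3, and 6 months after the epidural steroid injection") and lacks that label. Section D1 then says "Group differences in the improvement scores at the 12 month time point and at the intermediate time points will be analyzed" by Mann-Whitney, with no rule for multiple tests.

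**Precedence.** The SAP, dated after the IRB approval date, does not say that it refines or replaces the protocol's primary outcome. The protocol does not defer to a SAP. The general outcome statements in the protocol abstract and the SAP introduction name no time point.

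**Timing.** Protocol Section 7 has the questionnaire completed "again four weeks after their first injection, a time point at which patients routinely have a follow-up visit"; SAP Sections B, E and G and Table 2 use 2 weeks. Protocol Section 7 also counts the 3-month, 6-month and 1-year contacts from the second injection when one is recommended. SAP Section E and Table 2 count the 12-month score from the first injection.

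**The concern.** The two documents define different primary analyses. If an earlier visit gives p<0.05 and 12 months does not, Section 12 of the protocol supports reporting a positive primary result. SAP Aims 1 and 2 support reporting a negative primary result with a positive secondary one. Nothing written in advance settles the choice, so it could be made with the results in view.

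An early-only result is a realistic outcome here. Protocol Section 5 says "Randomized clinical trials of such treatments have often suggested that steroid injections are effective only in the short term".

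The clock matters for a second reason. A subject recommended for a second injection has one 1-year score. Protocol Section 7 collects it a year after that second injection, while the SAP analyses it as 12 months after the first. The recommendation is itself a study outcome (Protocol Section 12; SAP D2), so if eplerenone changes how often it is made, assessment timing will differ between the arms.

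**Working it through.** **1. The plan's own figure.** Inputs from Protocol Section 12: 20 per group, difference 9, SD 10, alpha 5% (taken as two-sided).

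- Sample size, normal approximation: n = 2(1.960 + 0.842)² × 10² / 9² = 19.4, so 20 per group.
- Power, normal approximation: 9 / (10 × √(2/20)) = 2.846; Φ(2.846 − 1.960) = 81%.
- Power, two-sample t-test: 79%. Mann-Whitney by simulation on normal data: 77%.
- A one-sided test would give n = 16 and 88.5% power, so the plan's figure is two-sided.

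The figure reproduces for **one** comparison, which matches the SAP's single primary time point.

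**2. How often the two readings diverge.** Assumptions: complete data, 20 per group, normal change scores with SD 10, four equally correlated visits, and an exact Mann-Whitney test at each visit (reject at U ≤ 127 or the mirror value; two-sided size 4.91%).

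The documents give no between-visit correlation. The range starts at 0.5 because D1 forms every improvement score by "subtracting the score at a given time point from the score obtained prior to the first epidural steroid injection". With equal score variances s² and a common correlation r, Cov(Xt − X0, Xs − X0) = s²(1 − r) and Var(Xt − X0) = 2s²(1 − r). The ratio is 0.5 for any r.

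Simulated results, 40,000 runs per null case and 20,000 per effect case:

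| Correlation between visits | 0.5 | 0.7 | 0.8 | 0.9 |
|---|---|---|---|---|
| No effect: an earlier visit significant, 12 months not | 10.8% | 8.4% | 6.8% | 5.0% |
| Same pattern, favouring eplerenone only | 5.6% | 4.1% | 3.4% | 2.4% |
| 9 points at every visit: an earlier visit significant, 12 months not | 19% | 16% | 14% | 10% |

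The second row comes from a separate run of 20,000. If instead a true 9-point effect exists at the first visit only, the divergent pattern appears in about 76% of trials across correlations 0.5 to 0.9.

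**3. Two success rules, for illustration.** Neither document states either rule.

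- Any one of four unadjusted tests counts: false-positive chance 15.5% / 13.3% / 11.7% / 9.8% at the four correlations.
- All four required: 0.1% at 0.5 and 1.6% at 0.9, both below 5%. With a true 9-point effect at every visit, joint power is about 50% at 0.5 and 65% at 0.9.

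The protocol wording therefore does not by itself fix an error rate.

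**4. The clock.** Protocol Section 7 puts the clinic's second-injection rate at about 30%; Sections 12 and 16 put the second injection about 4 to 6 weeks after the first. If that rate applied, 0.30 × 40 = 12 subjects would have a shifted 1-year score. The shift is 28/365 = 7.7% to 42/365 = 11.5% of the year. At 3 months (91 days) the same shift is 28/91 = 31% to 42/91 = 46% of the interval.

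**The case against.** The strongest reply is that the SAP already settles the matter. It names one primary time point, the principal investigator and statistician signed it after IRB approval, and a SAP is where a general protocol outcome is usually made specific. The trial is also a pilot, and its power statement fits one comparison. This carries weight: the SAP does read as a narrowing. But the contrary sentences in Protocol Section 12 still stand, and no text gives the SAP precedence.

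Other points stand in part:

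- The protocol does list its visits in Sections 7 and 16. What it lacks is a primary one among them.
- The null figures count both directions, and about half favour eplerenone. The table shows both counts.
- With 9 points at every visit, an early-only result reflects a missed true effect at 12 months. That row shows how often the label would be in dispute, not a false-positive rate.
- A correlation of 0.5 is not a strict floor. At 0.3 and 0, the any-of-four figure is about 17% and 18%.
- The two-week versus four-week conflict does not touch a 12-month primary. The clock conflict does, but no bias from a shift of 4 to 6 weeks has been shown, and the 30% rate is for clinic patients generally.

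**Conclusion.** The concern holds and should be fixed. Following both documents gives two different primary analyses, and the 12-month label does not match how the protocol collects that score for subjects recommended a second injection.

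The two readings would disagree in roughly 5% to 11% of trials with no effect and 10% to 19% with a constant 9-point effect. They would disagree in most trials if the benefit were confined to the first visit. These sizes rest on assumed correlations, complete data and normal change scores. The contradiction itself rests only on the text. The stated 5% and 80% are not in error for a single comparison.

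**What to change.** Before unblinding, amend both sentences in Protocol Section 12 (the primary analysis and the primary outcome line) to name the 12-month change as the sole primary comparison, as SAP Aim 1 does. Attach the power statement to that comparison and label the earlier visits secondary in both documents.

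In the same amendment:

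- Reconcile the first follow-up time across Protocol Sections 7 and 16 and SAP Sections B, E, G and Table 2.
- State one clock for the 12-month score in both documents. The first injection is the one every subject has, and SAP Section E and Table 2 already use it.
- Report scores already collected on the other clock with their actual timing.

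**Cost.** A short protocol amendment and small SAP edits, with no added subjects or questionnaires. An early-only result could no longer be presented as primary. If the benefit is short-lived, a 12-month primary could miss it, and the investigators should accept that knowingly. Counting from the first injection changes the contact schedule for subjects recommended a second one, and scores already collected cannot be re-timed.

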Statistical Analysis Plan

Epidural Steroid Injection with Supplemental Oral Eplerenone for Low Back Pain: A Prospective, Double Blind Randomized Trial

Principal Investigator: [name]

Project Sponsor: Department of Anesthesiology, University of Cincinnati College of Medicine

UC IRB Number: 2017-2713

[figure not shown]
IRB Approval Date(s): 10/11/2017

SAP Date (PI Signature Date): 1-17-18

Version: Original

Statistician(s): [name]

[figure not shown]
This SAP has been reviewed and approved by:

[name], Principal Investigator

1-17-2018

Date

[name], Statistician

1-17-2018

Date

A. Introduction:

Low back pain is a leading cause of disability and health care costs in the United States, and treatments are ineffective for many patients. Epidural steroid injections are a common treatment, but their efficacy has been questioned and for many patients they do not provide complete relief. We hypothesize, based on preclinical studies, that lack of complete efficacy may be due to the fact that clinically used steroids activate not only the intended drug target, the glucocorticoid receptor (GR), but also the pro-inflammatory mineralocorticoid receptor (MR). To test this hypothesis, this pilot study will recruit patients scheduled for lumbar epidural steroid injections for degenerative disc disease, and randomize them to receive a concurrent treatment with oral eplerenone (a clinically approved antagonist of the mineralocorticoid

receptor) or placebo for 10 days starting just after the epidural injection. The primary outcome will be improvement in treatment outcome as measured by the Oswestry Low Back Pain Disability Questionnaire, a validated research instrument that investigates both pain and functional outcomes. Subjects will be followed for one year. Secondary outcomes include the clinical course, in particular, whether the patient requires additional injections or not as part of their routine clinical care.

B. Specific Aims and Hypotheses

Aim 1: Test the hypothesis that subjects receiving eplerenone will show greater improvement in the Oswestry Low Back Pain Disability Questionnaire 12 months after the epidural steroid injection than subjects receiving placebo (primary outcome measure).

Aim 2: Test the hypothesis that subjects receiving eplerenone will show greater improvement in the Oswestry Low Back Pain Disability Questionnaire at earlier time points (2 weeks, 3, and 6 months after the epidural steroid injection) than subjects receiving placebo.

Aim 3: test the hypothesis that subjects receiving eplerenone will have better clinical outcome of their epidural steroid injection than subjects receiving placebo.

C. Study Design

The University of Cincinnati Department of Anesthesiology has two suburban pain clinics that will serve as sources for recruiting subjects, UC Health Pain Medicine Center (Midtown) and UC Health Pain Medicine Center (West Chester).. Our target number for study enrollment is 40 subjects (20 per group). We have obtained authorization for 60 subjects, in order to allow for subjects who drop out. Patients evaluated for degenerative disc disease are routinely given an epidural steroid injection as part of their treatment regimen. Often this is the preferred treatment; if there is no clear indication for surgical intervention, a more conservative approach is sought prior to considering surgery.

Eplerenone and placebo pills with blinded labels will be provided by Investigational Drug Pharmacy. We will use a block-stratified randomization schedule with blocks of sizes 2 and 4. The West Chester and Uptown locations will have separate randomization schedules. Patients will be randomized to receive either eplerenone or placebo, which will be taken for 10 days starting two days after the epidural injection. The dose of eplerenone will be 50 mg PO daily. Eplerenone is extensively metabolized with less than 5% excreted unchanged in the urine. Thus, renal dysfunction has little effect on eplerenone pharmacokinetics. However, patients with compromised renal function may be at greater risk for hyperkalemia when taking eplerenone. For this reason, a blood sample will be obtained from each participant to verify inclusion criteria related to kidney function (see below) based on a basic metabolic panel performed the day of the procedure. Subjects with elevated potassium or creatinine will not be included in the study. The blood sample will be obtained just prior to the epidural injection, at the clinical laboratories located within (West Chester site) or adjacent to (Midtown clinic) the participating pain clinics. This will allow the results (metabolic panel including K⁺ and creatinine level) to be available by the following day. In order to avoid having subjects make an additional trip to the clinic, subjects will receive their study medications via overnight delivery service, once their blood test

results have been reviewed. Alternatively, subjects who prefer may return to the clinic to pick up their medications. A single take-home sheet of information about the study medication will be given to each patient along with the medication, to help reinforce these directions. We anticipate that few subjects will be excluded on the basis of their blood test.

Patients are normally seen for follow-up approximately one month after an epidural injection. Subjects who are recommended to have a second epidural injection at this follow-up visit will receive a second dose of the same study medication they received after their first injection. The same protocol will be followed: such subjects will have a repeat blood draw and re-confirmation of inclusion parameters prior to restarting the medication. Subjects who become ineligible at the time of the second injection will not receive a second round of study medication, but will continue to complete questionnaires and their data will be retained for analysis.

All patients will receive the same epidural steroid and approach (interlaminar injection of Kenalog (triamcinolone) and saline) as part of their standard care. Triamcinolone has a substantial potency for the MR in addition to the GR; all of the steroids commonly used for epidural injections show some activity at the MR. The procedures and drug are routinely used at the participating clinics for treatment of degenerative disc disorders.

We will use the REDCap (Research Electronic Data Capture) system for secure web based capture of questionnaire data, which is required in order to protect the confidentiality of the subjects' data.

Inclusion criteria:

- Adult patients of either sex, age 18 to 65
- Scheduled for lumbar epidural steroid injection as part of routine clinical care
- Have a diagnosis of lumbar degenerative disc disease demonstrated on either lumbar X-Ray or lumbar MRI.
- Have unilateral radicular symptoms or electromyograph consistent with radiculopathy and exam findings corresponding to this diagnosis: with symptoms reflecting a dermatomal distribution of pain and positive response to straight leg raise test, which is known to be a sensitive, but not specific test for nerve root irritation.

Exclusion criteria: Excluded from the study will be patients with medical contraindications, including specifically those related to use of eplerenone:

- Unable to complete questionnaires or give informed consent in English
- Unavailable for follow-up contacts to complete questionnaires
- Renal impairment (estimated glomerular filtration rate (GFR)<50 mL/min or serum creatinine >1.8mg/dL) on metabolic panel obtained just prior to epidural injections.
- Elevated serum potassium (>5.5 mEq/L) on metabolic panel obtained just prior to epidural injections.
- Have undergone previous lumbar surgery.

- Treated with oral steroids or injectable steroid within the past year.
- Diabetic
- Systolic blood pressure reading less than 100 mm Hg at most recent clinic visit.
- Prescribed protease inhibitors, a class of antiviral drugs widely used to treat HIV/AIDS and Hepatitis C.
- Taking strong CYP3A4 inhibitors
- Taking potassium supplements or potassium-sparing diuretics (amiloride, spironolactone, or triamterene) or using salt substitutes that contain potassium
- Lactating.
- Pregnant
- .

D. Statistical Analysis Plan

For categorical variables, counts and percentages will be presented. As a check on randomization, groups will be compared using the Fisher's exact test. For continuous variables, mean, median, standard deviation (SD) and inter-quartile range (IQR) will be presented. Groups will be compared using the t-test, except that non-parametric methods will be used for ordinal variables or variables distributed non-symmetrically.

D1. Aims 1 and 2:

Each Oswestry response has 6 ordinal response choices scored 0 through 5. With 10 items and with the lowest score (0) representing the least disability, the total raw score ranges from 0 to 50. The score is expressed as a percentage of the maximum possible score. If a subject omits one question, the percentage score is based on a maximum score of 45. If a subject omits more than one question the questionnaire is considered invalid and the data not used. Improvement scores are calculated by subtracting the score at a given time point from the score obtained prior to the first epidural steroid injection. Group differences in the improvement scores at the 12 month time point and at the intermediate time points will be analyzed using the Mann-Whitney test.

Patients who are withdrawn from the study due to the initial blood test results will be considered as screening failures; no follow-up data or questionnaire scores will be obtained.

D2. Aim 3: The clinical outcome of the first epidural steroid injection will be abstracted from the medical chart record of the follow-up visit that occurs approximately 1 month after the injection, and will be summarized as an ordinal variable scored as: 1 adequate pain relief, no further treatment recommended; 2, partial relief, second injection recommended; 3 little pain relief, alternative treatment recommended.

Demographic data will be compared between the groups to determine if values differ significantly despite randomization (table 1 below).

E. Variables in the analysis data set

Patient unique ID
Age at first epidural steroid injection (years)
Date of epidural steroid injection
Weight and height at time of epidural steroid injection
Date of enrollment
Gender
Race
Ethnicity
Randomized to control or experimental group?
Oswestry scores (prior to first injection, 2 week, 3, 6, and 12 month post first injection)

F. Variables to Create / Calculate

BMI
Change in Oswestry score (score at each time point minus baseline score)

G. Data Sources

- EPIC chart review
- Oswestry scores exported from REDCap (baseline, 2 week, and 3, 6, and 12 month after first epidural steroid injection)

H. Software Used (with References) and Specialized Macros (with References)

Calculation of basic statistical parameters, t-tests, Mann-Whitney tests, and Fischer's exact test will be conducted using GraphPad Prism (GraphPad Software, Inc.) or SAS 9.4 (SAS Institute).

I. Mock tables to be produced

Table 1: Descriptive table of demographics of experimental and control groups prior to intervention.

Description	Control (N = ***) ¹	Experimental (N = ***) ¹	p value
Age at time of first injection (years)			
Weight at time of first injection			
Height at time of first injection			
BMI at time of first injection			
Race			
Ethnicity			
Oswestry score at first injection			

¹Mean, SD, median, interquartile range for continuous variables, number and % per group for categorical variables.

Table 2 Pain and disability outcomes

Description	Control (N = ***)	Experimental (N = ***)	p value
Change in Oswestry score at 2 weeks after injection			
Change in Oswestry score at 3 months after first injection			
Change in Oswestry score at 6 months after first injection			
Change in Oswestry score at 12 months after first injection			
Clinical outcome of first injection ³			

³ Converted to ordinal scale 1 – 3
